8.2 Deaths

All subject deaths (Grade 5 TEAEs) will be summarized for all subjects in the Safety population.

Deaths will be summarized in 5 main categories as follows:

- All deaths
- Deaths within 30 days of last dose
- Deaths within 31 to 100 days of last dose
- Deaths within 100 days of last dose
- Deaths more than 100 days from last dose

In addition, under each category causality to study disease and relationship to study treatment will also be summarized.

All reported subject deaths will be listed.

8.3 Adverse Events of Special Interest

Adverse events of special interest (AESIs) consist of immune-mediated AEs associated with immune checkpoint inhibitor therapies, cases of potential drug induced liver injury (DILI) and suspected transmission of an infectious agent by the study treatment. Analysis of DILI is discussed in Section 8.4 and cases transmission of infectious agent by study treatment, if any, will be discussed in patient narratives.

Immune checkpoint inhibitor therapy is complicated by side effects known as immune-mediated adverse events classified as AESIs. The sponsor has defined a set of events to track these adverse events known to be associated with immune checkpoint inhibitors that have potentially serious consequences or were determined to warrant ongoing routine surveillance. Each AESI is a grouped clinical term comprising a set of pre-defined AE preferred terms for potentially immune-related events that are related pathophysiologically and provide a consistent, reproducible, and transparent compilation of safety information over time. The specific list of preferred terms employed for analyses will be provided in the clinical study report.

The following summaries will be provided for AESIs for the P-Safety and Safety Populations. These summaries will be for all AESIs during the extended safety observation period.

TEAE included	Row-levels (sorted by)	Columns
Subject Incidence by SOC, Preferred Term and Severity		
All AESIs	AESI and PT (AESI, PT within AESI by descending frequency)	Worst severity: All Grades, Grade 3-4, Grade 4, Grade 5
AESIs leading to discontinuation of any treatment component	AESI and PT (AESI, PT within AESI by descending frequency)	Worst severity: Grade ≥ 3 , Grade 3, Grade 4, Grade 5
AESIs leading to discontinuation of all treatment components	AESI and PT (AESI, PT within AESI by descending frequency)	Worst severity: Grade ≥ 3 , Grade 3, Grade 4, Grade 5
AESIs leading to discontinuation of IV treatment components	AESI and PT (AESI, PT within AESI by descending frequency)	Worst severity: Grade ≥ 3 , Grade 3, Grade 4, Grade 5
AESIs leading to dose delay/reduction of any treatment component	AESI and PT (AESI, PT within AESI by descending frequency)	Worst severity: Grade ≥ 3 , Grade 3, Grade 4, Grade 5
AESIs leading to dose delay/reduction of all study treatment components	AESI and PT (AESI, PT within AESI by descending frequency)	Worst severity: Grade ≥ 3 , Grade 3, Grade 4, Grade 5
AESIs leading to dose delay/reduction of IV treatment component	AESI and PT (AESI, PT within AESI by descending frequency)	Worst severity: Grade ≥ 3 , Grade 3, Grade 4, Grade 5
AESIs leading to initiation of immune-modulating medication	AESI and PT (AESI, PT within AESI by descending frequency)	Worst severity: Grade ≥ 3 , Grade 3, Grade 4, Grade 5
AESIs leading to initiation of high dose of immune-modulating medication (defined in Section 6.4)	AESI and PT (AESI, PT within AESI by descending frequency)	Worst severity: Grade ≥ 3 , Grade 3, Grade 4, Grade 5
AESIs leading to initiation of immune-modulating medication and IV treatment discontinuation	AESI and PT (AESI, PT within AESI by descending frequency)	Worst severity: Grade ≥ 3 , Grade 3, Grade 4, Grade 5
All serious AESIs	AESI and PT (AESI, PT within AESI by descending frequency)	Worst severity: All Grades, Grade 3-4, Grade 4, Grade 5
Serious AESIs leading to initiation of immune-modulating medication	AESI and PT (AESI, PT within AESI by descending frequency)	Worst severity: Grade ≥ 3 , Grade 3, Grade 4, Grade 5

TEAE included	Row-levels (sorted by)	Columns
Serious AESIs leading to initiation of high dose of immune-modulating medication	AESI and PT (AESI, PT within AESI by descending frequency)	Worst severity: Grade >=3, Grade 3, Grade 4, Grade 5
Time to Event (per KM method only among those with event)		
AESIs	Time to first onset of AESIs by Group Term	
AESIs leading to initiation of immune-modulating medication	Time to first onset of AESIs by Group Term	
AESIs leading to initiation of high dose immune-modulating medication	Time to first onset of AESIs by Group Term	

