Table 9: Dose Interruptions of Atezolizumab

Assigned dose	Dose Interruptions
1200-mg atezolizumab IV q3w	At any time to manage unacceptable AESIs

AESI, adverse events of special interest; q3w, once every 3 weeks;

Table 10: Dose Modifications for Atezolizumab-Associated Adverse Events

CTCAE v5 Grade	Recommended Management
Grade 1 immune-mediated myelitis*	Delay treatment with atezolizumab
Grade 1 pericarditis**	Treatment may be resumed in subjects following recovery to Grade 0-1
Grade 2 myocarditis	
Grade 1 ^a - 2 pneumonitis	* Continue atezolizumab unless symptoms worsen or do not improve.
Grade 2 nephritis	
Transaminases (ALT or AST):	** Withhold treatment with atezolizumab and conduct a detailed cardiac evaluation to determine the etiology and manage accordingly.
• Increases to between $> 3 \times$ ULN and $\leq 10 \times$ ULN (from baseline values \leq ULN), or	
• Increases to between $> 5 \times$ ULN and $\leq 10 \times$ ULN (from baseline values between $>$ ULN and $\leq 3 \times$ ULN), or	
• Increases to between $> 8 \times$ ULN and $\leq 10 \times$ ULN (from baseline values between $> 3 \times$ ULN and $\leq 5 \times$ ULN)	

CTCAE v5 Grade	Recommended Management
Grade 2 immune-mediated neuropathy (any cranial nerve disorder, including facial paresis, should be managed as per Grade 2 guidelines)***	Delay treatment with atezolizumab Treatment may be resumed in subjects following recovery to Grade 0-1.
Grade 2 or 3 diarrhea or colitis	
Grade 2 or 3 myositis	
Symptomatic adrenal insufficiency, hypothyroidism, or hyperthyroidism; Grade 2 or 3 hypophysitis; or Grade 3 or 4 hyperglycemia	*** For general immune-related neuropathy, if the event resolves to Grade 1 or better, resume atezolizumab. For facial paresis, if event resolves fully, resume atezolizumab; if event does not resolve fully while withholding atezolizumab, permanently discontinue atezolizumab.
Grade 2 ocular inflammatory toxicity	
Grade 2 or 3 pancreatitis or Grade 3 or 4 increases in amylase or lipase levels	
Grade 3 or 4 infection	
Grade 2 infusion-related reactions or cytokine release syndrome	
Grade 3 rash	
Suspected Stevens-Johnson syndrome or toxic epidermal necrolysis (any grade)	
Other Grade 2 or 3 atezolizumab-associated AEs	
Grade 2 - 4 immune-mediated myelitis	Permanently discontinue atezolizumab
Grade 3 or 4 immune-mediated neuropathy, including facial paresis	
Grade 2 - 4 myocarditis	
Grade 4 myositis and/or recurrent Grade 3 myositis	
Grade 3 or 4 pneumonitis	

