6.6.2.2.2. Immune-Related Pulmonary Events

Pulmonary events may present as new or worsening cough, chest pain, fever, dyspnea, fatigue, hypoxia, pneumonitis, and pulmonary infiltrates. Subjects should be assessed for pulmonary signs and symptoms throughout the study and will also have CT scans of the chest performed at every tumor assessment.

All pulmonary events should be thoroughly evaluated for other commonly reported etiologies, such as pneumonia or other infections, lymphangitic carcinomatosis, pulmonary embolism, heart failure, chronic obstructive pulmonary disease, or pulmonary hypertension. COVID-19 evaluation should be performed per institutional guidelines where relevant. Management guidelines for pulmonary events are provided in [Table 15](#).

Table 15: Management Guidelines for Immune-Related Pulmonary Events, Including Pneumonitis

Severity of Event	Management
Grade 1	
 Continue atezolizumab and monitor closely. Re-evaluate on serial imaging. Consider subject referral to pulmonary specialist. For Grade 1 pneumonitis, consider withholding atezolizumab.
Grade 2	
 Withhold atezolizumab for up to 12 weeks after event onset.^a Refer subject to pulmonary and infectious disease specialists and consider bronchoscopy or BAL with or without transbronchial biopsy. Initiate treatment with 1–2 mg/kg/day oral prednisone or equivalent. Resume atezolizumab if event resolves to Grade 1 or better.^b Permanently discontinue atezolizumab and contact the Sponsor if event does not resolve to Grade 1 or better while withholding atezolizumab.^{c,d} For recurrent events or events with no improvement after 48–72 hours of corticosteroids, treat as a Grade 3 or 4 event
Grade 3 or 4	
 Permanently discontinue atezolizumab and contact the Sponsor.^c Oral or IV broad-spectrum antibiotics should be administered in parallel to the immunosuppressive treatment. Bronchoscopy or BAL with or without transbronchial biopsy is recommended. Initiate treatment with 1–2 mg/kg/day IV methylprednisolone or equivalent. If event does not improve within 48 hours after initiating corticosteroids, consider adding an immunosuppressive agent. If event resolves to Grade 1 or better, taper corticosteroids over ≥ 1 month.

BAL, bronchoscopic alveolar lavage.

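### Eleven of the 13 AESI incidence tables in SAP 8.3 report only Grade 3 or higher, although the protocol directs delay, steroids and some discontinuations at Grade 2 or any grade

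*SAP*

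**What the plan says.** SAP 8.3 introduces its AESI tables with the statement "These summaries will be for all AESIs during the extended safety observation period". Two of the 13 incidence tables, for all AESIs and for all serious AESIs, have the columns "Worst severity: All Grades, Grade 3-4, Grade 4, Grade 5". The rows that describe what was done about an AESI do not. For example, "AESIs leading to discontinuation of any treatment component" has "Worst severity: Grade ≥ 3 , Grade 3, Grade 4, Grade 5", and "AESIs leading to initiation of immune-modulating medication" has the same set, without All Grades. The SAP gives no reason for the difference.

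The protocol ties these actions to lower grades as well. In Protocol 6.6.1, Table 10, the block that delays atezolizumab includes "Grade 2 nephritis", and the block that stops it permanently includes "Grade 2 - 4 immune-mediated myelitis". In Protocol 6.6.2.2.2, Table 15, the instruction for a Grade 2 pulmonary event is to withhold atezolizumab and "Initiate treatment with 1–2 mg/kg/day oral prednisone or equivalent".

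**The concern.** A reader who wants to know how often pneumonitis, nephritis or colitis interrupted or ended treatment, or needed steroids, will go to the AESI action tables. AESI groups exist to bring related preferred terms together so that this question has one answer per group. If the action tables start at Grade 3 while the protocol's own management guidance starts at Grade 2 for many events, a delay or steroid course given exactly as the protocol directs can be missing from the table that carries its name. The steroid rows add a second problem: two outputs in the same section, labelled alike, would describe different sets of subjects.

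**Working it through.** No design figure is at issue, so the check is a comparison of tables and rules. The counts below are of tables and rules, not of patients.

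**1. Columns of the SAP 8.3 incidence tables**

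| Rows | Tables | All Grades column |
|---|---|---|
| All AESIs; all serious AESIs | 2 | yes |
| Discontinuation (any, all, IV treatment) | 3 | no |
| Delay or reduction (any, all, IV treatment) | 3 | no |
| Immune-modulating medication (any; high dose; with IV discontinuation) | 3 | no |
| Serious AESIs with immune-modulating medication (any; high dose) | 2 | no |

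Tables without All Grades: 3 + 3 + 3 + 2 = 11 of 13.

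**2. Protocol Table 10, delay block (17 rows)**
- 14 rows include Grade 2 or lower, or carry a trigger without a Grade 3 floor. Of these, 8 apply only at Grade 2 or lower. One of the 8, Grade 1 myelitis, is footnoted to continue unless symptoms worsen or fail to improve.
- 2 rows are Grade 3 or higher only, and 1 (transaminases) is set by multiples of the upper limit of normal. Check: 14 + 2 + 1 = 17.
- Protocol 6.6.2.2.14 also delays atezolizumab for any other immune-related event at Grade 2 or 3.

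**3. Protocol Table 10, permanent discontinuation block (16 rows)**
- 5 rows explicitly include Grade 2 or any grade: myelitis; myocarditis; the row for myasthenia gravis, Guillain-Barré and meningoencephalitis; recurrent pancreatitis; and confirmed Stevens-Johnson syndrome or toxic epidermal necrolysis.
- 1 row (recurrent hypophysitis) gives no grade for the recurrence, 9 are Grade 3 or higher only, and 1 is set by liver-enzyme and bilirubin multiples. Check: 5 + 1 + 9 + 1 = 16.
- Grade 2 myocarditis stands in both the delay and the discontinuation block. Those entries must be reconciled, but the point here does not depend on how.

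**4. Steroids**
- The protocol gives 1–2 mg/kg/day at Grade 2 for pulmonary events (Table 15) and renal events (Table 24), and at Grade 2 or 3 for hypophysitis (Table 17) and pancreatitis (Table 23).
- SAP 6.4 defines high dose as at least 40 mg/day of prednisone or equivalent. At 1 mg/kg/day the weight that reaches it is 40 ÷ 1 = 40 kg. A 60 kg subject takes 60 × 1 = 60 mg/day.
- A Grade 2 pneumonitis treated per Table 15 would therefore usually meet the SAP's high-dose definition and still be absent from the high-dose AESI incidence table.

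**5. Where the lower-grade actions do appear**
- SAP 8.1: All Grades tables by preferred term for discontinuation, hold, delay, reduction and modification.
- SAP 6.4: immune-modulating medication for AESIs, without a grade limit, by drug class and name.
- SAP 8.3: time to first onset of AESIs leading to such medication, and to high-dose medication, by AESI group and without a grade limit.
- SAP 8.1: a listing of all AESIs with grade and action taken.

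Preferred-term counts do not add up to a group count. If two terms in one AESI group have a and b subjects, the group has anything from max(a, b) to a + b, because one subject can have both. The 6.4 summary is by drug, not by event. The time-to-onset summaries describe timing among subjects with the event. Even if the shell prints their number, there is no counterpart for delay or discontinuation.

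**6. Share omitted**

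Let g be the share of subjects with the action whose worst grade is 1 or 2. The table then shows 1 − g of them. The documents do not give g. As an assumed range, g = 20%, 50% or 80% means the table shows 80%, 50% or 20%.

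**The case against.** The strongest reply is that little is hidden. Every lower-grade action is counted or listed somewhere, as step 5 shows, and the 60 kg subject is in the 6.4 high-dose summary and in the high-dose time-to-onset summary. The tables are descriptive, no formal safety comparison is planned, and no decision rule uses them. All of this stands, and it limits the point to a missing view of the data.

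Some stronger readings are tempting, and the documents do not support them:
- A reader might infer that most such actions are omitted. No grade distribution is given, and 9 of the 16 discontinuation rows in Table 10 apply only at Grade 3 or higher. The columns also use worst severity, so a Grade 2 event that later worsens is still counted.
- A reader might infer that the protocol mandates these actions at Grade 2 or lower. Table 10 presents its actions as recommended. The general guidance in Protocol 6.6.2.2 is to consider holding for most Grade 2 toxicities, and Grade 1 is generally continued.
- A reader might infer that the tables flatter the combination arm. The cut is the same in every arm. The AESI list in Protocol Table 31 includes hepatitis, hyperthyroidism and pancreatitis, and the rows for any treatment component can include actions on cabozantinib or sorafenib alone. Only the IV rows must fall in the combination arm, the one arm that receives atezolizumab.

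What the reply does not meet is the grouped count. None of the other outputs gives the all-grade subject incidence by AESI group for delay, discontinuation or immune-modulating medication.

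**Conclusion.** The point holds as a reporting gap. Eleven of 13 AESI incidence tables stop at Grade 3 without a stated reason, against a lead-in that covers all AESIs and a protocol that directs delay and steroids at Grade 2 for many events and discontinuation at Grade 2 or any grade for some. Two consequences follow from the text alone: the all-grade subject incidence by AESI group is not produced for these actions, and the immune-modulating-medication incidence tables do not match the ungraded time-to-onset summaries beside them. The size in patients is unknown. It equals the share of actions with worst grade 1 or 2, which the documents do not give. No efficacy result, error rate or stopping decision is affected.

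**What to change.** Add an All Grades column to the 11 AESI tables for discontinuation, delay or reduction, and immune-modulating medication, including the two serious-AESI rows. Keep the planned columns for Grade 3 or higher, Grade 3, Grade 4 and Grade 5. This matches the all-grade reporting in SAP 8.1 and puts the medication tables on the same footing as their time-to-onset summaries. The grade, the action taken and the medication are already collected, so the cost is a change to the table shells and their programs, with no new data.

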13. Corrected QT interval calculated by the Fridericia formula ($QTcF > 480$ ms per electrocardiogram (ECG) within 14 days before randomization.

Note: If a single ECG shows a $QTcF$ with an absolute value > 480 ms, two additional ECGs at intervals of approximately 3 min must be performed within 30 min after the initial ECG, and the average of these three consecutive results for $QTcF$ will be used to determine eligibility

14. History of psychiatric illness likely to interfere with ability to comply with protocol requirements or give informed consent

15. Pregnant or breastfeeding females.

16. Inability to swallow tablets.

17. Previously identified allergy or hypersensitivity to components of the study treatment formulations or history of severe hypersensitivity to monoclonal antibodies. Subjects with rare hereditary problems of galactose intolerance, the Lapp lactase deficiency or glucose-galactose malabsorption are also excluded.

18. Any other active malignancy at time of randomization or diagnosis of another malignancy within 2 years before randomization that requires active treatment, except for superficial skin cancers, or localized, low grade tumors deemed cured and not treated with systemic therapy.

ESTIMATED LENGTH OF SUBJECT PARTICIPATION

It is estimated that subjects will receive study treatment for an average of approximately 6 months. Subjects will be followed until death, withdrawal of consent for non-interventional study assessments, or Sponsor decision to no longer collect survival data.

ESTIMATED STUDY DATES

It is estimated that approximately 25 months will be required to randomize 740 subjects at approximately 250 global sites for the global enrollment phase of the study. The number of events required for the final analyses of the primary PFS (257 events among the first 372 randomized subjects within the cabozantinib + atezolizumab combination and sorafenib arms) and primary OS (368 events among the 555 randomized subjects within the cabozantinib + atezolizumab combination and sorafenib arms) is expected to be observed around approximately 18 months and around 38 months, respectively, after the first subject is randomized.

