2.3 Power and Sample Size Justification

The study is designed to provide adequate power for analyses of both primary endpoints of PFS and OS comparing the experimental arm (cabozantinib + atezolizumab) with the control arm (sorafenib), and for the analysis of the secondary endpoint of PFS comparing single-agent cabozantinib with the control arm. For the primary endpoints, a larger sample size is needed to provide reasonable power for OS than is required to evaluate PFS. As a result, if PFS were to be evaluated in the entire study sample, the PFS events may be biased toward shorter progression times. Thus, to allow longer, more robust PFS follow up among a smaller number of subjects, this study employs a “trial within a trial design” (Hessel C, 2016).

Per protocol amendment 2, the total sample size was 740 subjects, to be randomized in a 2:1:1 fashion: 370 to the experimental combination arm (cabozantinib + atezolizumab), 185 to the control arm (sorafenib), and 185 to the single-agent cabozantinib arm.

Per addendum to the protocol amendment 2, the sample size for the global study was increased to ensure the enrollment of at least 185 subjects in the single agent cabozantinib arm in order to allow for enrollment of the protocol-specified number of subjects in this arm. The analyses are to be carried upon observance of the specified number of events as stated in the protocol.

For PFS, a total of 257 events in the first 372 subjects randomized in a 2:1 ratio in the experimental and control arms (n=248 and 124 respectively; the PITT population) provide the study with 90% power for a 2-sided log-rank test with a 1% level of significance to detect a hypothesized true HR of 0.6. Assuming an exponential distribution of PFS, this corresponds with a 67% increase in median PFS from 3.6 months to 6.0 months. The minimum observed effect that would result in statistical significance for PFS is an HR of 0.71, a 41% improvement in median from 3.6 to 5.1 months. Interim analysis of PFS is not planned.

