4.6.2 Extended Observation Period

To evaluate the incidence of adverse events of special interest (AESIs), extended observation periods are defined for summarizing safety data as below.

Core Treatment Period:

- Date of last dose of last component study treatment + 100 days or
- Date of death or
- Date subject withdrew consent for non-interventional study assessments or
- Data cutoff date for analysis under consideration

Crossover Treatment Period:

- Date of last dose of last component study treatment + 100 days or
- Date of death or
- Date subject withdrew consent for non-interventional study assessments or
- Data cutoff date for analysis under consideration or
- Date of initiation of maintenance phase -1

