8 SAFETY SUMMARIES

Safety summaries will include all subjects in the Safety and P-Safety populations. Data to be included for Core and Crossover Periods and the treatment arm groupings for the summaries are described in Section 4.6. No formal statistical comparison between the experimental and control arms is planned.

Safety and tolerability will be assessed by the incidence of treatment emergent-adverse events (TEAEs), changes in laboratory parameters and vital signs from baseline, and ECOG PS.

An Independent Data Monitoring Committee (IDMC) will monitor safety of the subjects during the study on a regular basis. The committee will operate independently from the Sponsor and the clinical investigators.

The primary responsibility of the IDMC is to review the accumulating safety data on a regular and an ad hoc basis and make recommendations to the Sponsor regarding the continued conduct of the study. Safety data will be provided at regular intervals to the IDMC in the form of summary reports or data listings from the Sponsor or its designated representative.

Details regarding IDMC membership, schedule and format of meetings, format for presentation of data, access to interim data, method, and timing of providing interim reports to the IDMC, and other issues relevant to committee operations are described in the IDMC charter.

The IDMC members will use their expertise, experience, and judgment to evaluate the safety data from the trial and to recommend to the Sponsor whether the trial should continue or be stopped early for safety. No formal statistical rules recommending early stopping for safety are planned.

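### SAP 8.3 estimates time to first AESI only among affected subjects, so the onset figures depend on length of observation and cannot be compared between arms or data cutoffs

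*SAP*

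**What the plan says.** The table in SAP 8.3 ends with a block headed "Time to Event (per KM method only among those with event)". It has three rows: all AESIs, AESIs leading to immune-modulating medication, and AESIs leading to high-dose immune-modulating medication. Each is specified as "Time to first onset of AESIs by Group Term".

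The text above the table sets the population and the window: "The following summaries will be provided for AESIs for the P-Safety and Safety Populations" and "These summaries will be for all AESIs during the extended safety observation period". SAP 4.6.2 gives the first end point of that window as "Date of last dose of last component study treatment + 100 days or", and then lists death, withdrawal of consent for non-interventional assessments, and data cutoff. It does not say which limit governs. I read it as the earliest, counted from first dose, as SAP 4.6.1 states for the standard period.

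The other rows of the table give AESI subject incidence without the restriction to affected subjects. SAP section 8 adds: "No formal statistical comparison between the experimental and control arms is planned". Section 8.3 plans no onset curve in all treated subjects, no cumulative incidence function and no exposure-adjusted AESI rate.

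**The concern.** Kaplan-Meier is useful because it credits follow-up without an event. Limiting it to subjects with the event discards that follow-up. What remains is the timing of those events that happened to fall inside each subject's window, and late events are the ones most often lost.

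Two groups with the same risk but different windows will therefore usually show different onset times. So will one group reported at two data cutoffs. SAP 4.1 plans up to six analyses and repeats the safety summaries, so both comparisons will be open to readers. Because the curve always ends at 100%, it also cannot show what share of treated subjects is affected by a given month. For a regimen containing a checkpoint inhibitor, that is a question readers will ask.

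**Working it through.** The documents state no AESI onset figure, so there is nothing to reproduce.

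**Inputs**
- Window extension: 100 days / 30.4375 = 3.285 months (SAP 4.6.2; month length from SAP section 4).
- Treatment time: the protocol synopsis gives one figure for all subjects, "It is estimated that subjects will receive study treatment for an average of approximately 6 months". As an assumption by arm I use exponential treatment time with the planning PFS medians (SAP 2.3: "this corresponds with a 67% increase in median PFS from 3.6 months to 6.0 months"). As a check that these are the design values, 3.6/6.0 = 0.60, and (2.576 + 1.282)² / [(2/3)(1/3)(ln 0.60)²] = 14.88/0.0580 ≈ 257 events, as stated.
- Cutoffs: 18.4 months with 16.5 months of accrual, and 38 months with 25 months of accrual (SAP 2.3), with uniform accrual assumed.
- AESI hazard h: 0.03, 0.06 and 0.12 per month. This is an assumption; the documents give none.
- Hazard shape: Protocol 8.3.1 says immune-related events mostly come in the first 12 weeks, with some later.

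**Closed form, constant hazard, no cutoff.** Let L = 3.285 and μ = ln 2 / median treatment time. The proportion with an observed onset by time t is 1 − e^(−ht) up to L. After L it is A + B[1 − e^(−(h+μ)(t−L))], where A = 1 − e^(−hL) and B = e^(−hL)·h/(h+μ). The median among affected subjects is where this equals (A+B)/2.

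For h = 0.06, A = 0.1789.
- Treatment median 3.6: μ = 0.1925, B = 0.1951, (A+B)/2 = 0.1870. Median = 3.285 − ln(1 − 0.0081/0.1951)/0.2525 = 3.45 months.
- Treatment median 6.0: μ = 0.1155, B = 0.2807, (A+B)/2 = 0.2298. Median = 3.285 − ln(1 − 0.0509/0.2807)/0.1755 = 4.42 months.

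Risk is identical in the two groups, yet the gap is 0.97 months. The unrestricted median at this hazard is ln 2/0.06 = 11.6 months.

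**All scenarios** (median onset among affected subjects, 3.6- vs 6.0-month group). The no-cutoff, constant-hazard, equal-risk row is from the closed form; the rest are simulations of 400,000 subjects per group.

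| Scenario | h = 0.03 | h = 0.06 | h = 0.12 |
|---|---|---|---|
| Constant hazard, no cutoff | 3.84 vs 5.25 | 3.45 vs 4.42 | 2.88 vs 3.40 |
| Constant hazard, 18.4-month cutoff | 3.02 vs 3.48 | 2.81 vs 3.18 | 2.44 vs 2.70 |
| Hazard falls to a quarter after week 12, no cutoff | 2.02 vs 2.39 | 1.95 vs 2.28 | 1.80 vs 2.06 |
| Same, 18.4-month cutoff | 1.78 vs 1.90 | 1.72 vs 1.83 | 1.61 vs 1.71 |
| All events within 12 weeks, no cutoff | 1.36 vs 1.35 | 1.32 vs 1.33 | 1.27 vs 1.27 |

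The last row shows no shift because the 100-day extension alone already covers week 12.

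**Unequal risk** (constant hazard, no cutoff, 0.03 in the 3.6-month group). If the 6.0-month group has 0.06, onset looks later there (3.84 vs 4.44). At 0.12 it looks earlier (3.83 vs 3.40), and at 0.30 much earlier (3.83 vs 1.98).

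**One arm, two cutoffs** (6.0-month treatment median, h = 0.06, 25-month accrual). Reported median onset moves from 3.1 months at the 18.4-month cutoff to 4.3 at 38 months. With the early-weighted hazard it moves from 1.8 to 2.2. Risk is unchanged throughout.

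**All treated subjects, with censoring** (h = 0.06, no deaths simulated). Cumulative probability is 16.5% vs 16.4% at 3 months and 30.2% vs 30.1% at 6 months. This matches 1 − e^(−0.18) = 16.5% and 1 − e^(−0.36) = 30.2%, so the artefact is gone.

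**The case against.** The case for leaving the rows alone has substance. The SAP states the restriction openly. Onset timing among affected subjects is a legitimate descriptive quantity, and without censoring Kaplan-Meier returns essentially the ordinary median. No test or hazard ratio on onset is planned. The same table reports AESI incidence in both safety populations: overall, serious, and by consequence for treatment. The share of subjects affected is therefore reported, though not by time. A reader who infers that the AESI reporting as a whole ignores subjects at risk would be wrong; that is true only of these three rows.

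A reader might also infer that the method will make onset look later in the experimental arm. The documents do not support that. They do not say which arm will be treated longer: the one duration estimate covers all subjects, and treatment may continue past progression. Only the experimental arm receives atezolizumab and these AESIs are largely checkpoint-inhibitor events, so equal hazards are not the natural expectation, and a higher hazard in that arm can reverse the shift.

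Nor should the size be taken from a shortcut that ends observation at last dose. With onset among affected subjects exponential at rate h + μ and h = 0.05, that gives ln 2/0.2425 = 2.86 vs ln 2/0.1655 = 4.19 months. It omits both the 100-day extension and the data cutoff that apply to these rows.

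What survives is narrower. The estimate mixes risk with window length, and section 8.3 offers nothing on timing that separates them. Crude incidence does not fill the gap, because it too rises with length of observation.

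**Conclusion.** The point holds as a minor one. The three rows describe onset timing in affected subjects and should not be compared between arms or between reports at different cutoffs.

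At equal constant hazard the spurious gap between groups is about 0.5 to 1.4 months without a cutoff and 0.26 to 0.46 months at 18.4 months. With an early-weighted hazard at that cutoff it is about 0.1 month. It is zero if all events fall within 12 weeks, and it reverses in some unequal-hazard cases. These sizes rest on assumed hazards, on PFS medians standing in for treatment time, and on exponential treatment time with uniform accrual. The dependence on window length does not rest on those values; it needs only that some events can occur after some windows have closed.

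Alpha, sample size and the efficacy endpoints are unaffected.

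**What to change.** For the same three rows, add cumulative incidence from first dose in all Safety and P-Safety subjects. Censor event-free subjects at the end of the extended safety observation period, treat death without the AESI as a competing event (Aalen-Johansen), and report by arm at fixed times such as 3, 6 and 12 months. Keep median onset among affected subjects as a plain descriptive statistic. Drop the Kaplan-Meier label from it and footnote that it is not for comparison between arms or cutoffs.

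Two limits belong in the footnotes. Cumulative incidence with death as a competing event also reflects differences in mortality, and censoring at the end of the window assumes that subjects whose window has closed resemble those still observed.

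The cost is a change of SAP wording, a few lines of code and a few extra safety outputs. No new data are needed.
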